#### Major Adverse Event (MAE)

For the purposes of this study, the definition of a major adverse event includes:

- Death
- Any major amputation performed on the target limb
- Clinically-driven target lesion revascularisation

#### 7.2 Adverse Event Reporting Requirements

#### 7.2.1 General Reporting Requirements

The following adverse events should be recorded on the eCRF through 36 months post-index procedure:

- All potentially device and/or procedure-related adverse events
- All major adverse events (MAE)
- All vascular adverse events in the target limb.

The report should include: description of event, severity, duration, action taken, treatment outcome and relationship of the adverse experience to the study device and/or procedure (i.e., unrelated, possibly related, related or relationship not assessable).

The following definitions for rating severity of adverse events will be used:

Mild: Awareness of signs or symptoms, but easily tolerated; are of minor irritant type; causing no loss of time from normal activities; symptoms would not require medication or a medical evaluation; signs or symptoms are transient.

Moderate: Interferes with the subject's usual activity and/or requires symptomatic treatment.

Severe: Symptom(s) causing severe discomfort and significant impact of the subject's usual activity and requires treatment.

All reportable events should be followed until resolution or the end of the study.

#### 7.2.2 Reporting Requirements for Serious and Major Adverse Events

All serious and potentially device and/or procedure-related, MAE and vascular adverse events in the target limb must be reported to the Sponsor within 24 hours of knowledge of the event or by the end of the next working day. This may be done via phone, fax, email or eCRF.

Sponsor will review all reported events for potential reporting in accordance with MEDDEV 2.12.1, Rev 8 (2013) "Guidelines on a Medical Devices Vigilance System". Sponsor may request medical record documentation (e.g., procedure notes, operative notes, discharge summary, relevant progress notes, imaging, or lab studies) to facilitate this review.

The Sponsor will determine whether all of the local Investigators need to be informed immediately of an SAE or UADE, or whether this can be postponed until the next regularly scheduled study update.

The Investigator is responsible for reporting applicable serious adverse events to their EC/IRB as required by EC/IRB procedures and local/national regulations. A copy of each EC/IRB safety report will be provided to Sponsor.

### 7.2.3 Device Failures and Malfunctions

All device observations / performance issues, malfunctions or failures of the Veryan BioMimics 3D stent, whether or not associated with an adverse event must be reported via the eCRF within 24 hours of knowledge of the event or by the end of the next working day.

Sponsor will review all reported events for potential reporting in accordance with MEDDEV 2.12.1, Rev 8 (2013) "Guidelines on a Medical Devices Vigilance System". Sponsor may request medical record documentation (e.g., procedure notes, operative notes, discharge summary, relevant progress notes, imaging, or lab studies) to facilitate this review.

### 8.0 RISK/BENEFIT ASSESSMENT

#### 8.1 Risks

The BioMimics 3D Stent System is being used in accordance with the approved CE Mark indication and Instructions for Use. As with all procedures that utilise techniques for introducing a catheter into a vessel, complications may occur. These complications as listed in the instructions for use include, but are not limited to:

- Allergic reaction to Nitinol
- Allergic/anaphylactoid reaction
- Amputation
- Aneurysm
- Angina/coronary ischemia
- Arrhythmia
- Arterial occlusion/restenosis of the treated lesion/vessel without reintervention
- Arterial occlusion/restenosis of the treated lesion/vessel with intervention
- Arterial occlusion/thrombus, near the puncture site
- Arteriovenous fistula
- By-pass surgery
- Death related to procedure
- Death unrelated to procedure
- Deployment failure
- Device failure
- Embolisation, arterial
- Embolisation, stent
- Fever
- Haematoma bleed at needle, device path: nonvascular procedure
- Haematoma bleed, puncture site: vascular procedure
- Haematoma bleed, remote site
- Haemorrhage/bleeding requiring a blood transfusion
- Hypersensitivity reactions
- Hypotension/hypertension
- Incorrect positioning of the stent requiring further stenting or surgery
- Infection/abscess formation at access site
- Intimal injury/dissection
- Ischemia requiring intervention
- Ischemia/infarction of tissue/organ
- Liver failure
- Local infection
- Myocardial infarction
- Open surgical repair

- Pain
- Pancreatitis
- Partial stent deployment leading to surgical repair
- Pneumothorax
- Pseudoaneurysm
- Pulmonary embolism
- Radiation injury
- Renal failure
- Respiratory arrest
- Septicaemia/bacteraemia
- Shock
- Spasm
- Stent fracture
- Stent kinking
- Stent malapposition
- Stent migration
- Stroke
- Thrombosis
- Tissue necrosis
- Venous occlusion/thrombosis, near the puncture site
- Worsened claudication/rest pain

### 8.2 Risk Minimization

As with any endovascular procedure, appropriate safety precautions will be followed. In addition, this Protocol provides additional steps to minimize risk to study subjects. These include the following:

- Investigator Selection & Training: All investigators are required to be appropriately qualified by education, training and expertise in peripheral interventional techniques and placement of intravascular stents.
- Subject Screening: Patient selection will be in accordance with the Protocol and the IFU. Patients with known contraindications e.g. history of intolerance or adverse reaction to antiplatelet and/or anticoagulation therapies, bleeding diathesis, severe hypertension or renal failure, known hypersensitivity to nickel-titanium will not be eligible for the Study.

### 8.3 Potential Benefits

Prior human clinical experience in a population of 60 subjects has validated that the BioMimics 3D Stent System can be used to safely and effectively stent the femoropopliteal arteries, resulting in acute and long term luminal patency. Clinical study populations are defined by eligibility criteria more restrictive than the device IFU which may limit the application of results to a broader population. The MIMICS-3D Study is intended to evaluate the safety and effectiveness of the BioMimics 3D Stent System in a larger "real-world" clinical population.

### 9.0 STATISTICAL ANALYSIS PLAN

The analysis of the data from this study will be primarily descriptive. Continuous endpoints will be summarized by N, mean, standard deviation, median, minimum, and maximum. Categorical or binary endpoints will be summarised by N and percentage with confidence intervals as appropriate. Kaplan Meier plots will be used to display and summarise time to event data.

The planned sample size for analysis is at least 500 patients which is believed to be adequate to provide an accurate characterisation of BioMimics 3D in a "real-world" clinical settings.

### 9.1 Analysis Population

- Intention-to-Treat (ITT) Analysis Set: includes all enrolled subjects.
- *Modified Intention-to-Treat (mITT) Analysis Set*: includes all enrolled subjects in whom the BioMimics 3D Stent System is implanted. Those subjects in whom the procedure is aborted without implantation of a stent will be excluded from this analysis set. This is the primary

analysis set for the primary safety and effectiveness endpoints, as well as secondary and exploratory endpoints.

• *Per-Protocol (PP) Analysis Set:* includes all enrolled subjects in whom the BioMimics 3D Stent System is implanted and who met all inclusion/exclusion criteria with no major protocol deviations. Those subjects in whom the procedure is aborted without implantation of a stent will be excluded from this analysis set. This is a secondary analysis set for the primary safety and effectiveness endpoints, as well as secondary endpoints.

While mITT is intended as the primary analysis set for all safety and effectiveness endpoints, the primary safety and effectiveness endpoints will additionally be evaluated in the ITT and PP analysis sets as supportive information. All subjects excluded from mITT analysis set will be described and the reasons for aborted procedures, if any, detailed.

A separate analysis will be conducted for the DCB cohort.

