### 3.0 STUDY PLAN

#### 3.1 Study Objective

The MIMICS-3D Study will evaluate safety, effectiveness and device performance within a real-world clinical population of patients undergoing femoropopliteal intervention.

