### 4.2 Secondary Outcome Measures

• Acute technical success defined as the achievement of a final residual diameter stenosis <30% at the end of the procedure

- Acute procedural success defined as both acute technical success and absence of the following adverse events: death, stroke, MI, acute onset of limb ischemia, index bypass graft or treated segment thrombosis, and/or need for urgent/emergent vascular surgery, within 72 h of the index procedure.
- Incidence of individual components of MAE (death, any major amputation performed on the index limb or CDTLR) at 30 days, 12, 24 and 36 months
- Overall rate and incidence of adverse events from Day 0 through completion of study follow-up at Month 36.
- Stent patency rate assessed by duplex ultrasound, as available, determined at Months 12, 24 and 36. This will be assessed using values of PSVR >2.0, >2.4; >2.5; and >3.5 each to indicate loss of patency on duplex ultrasound.
- Clinical outcome: comparison of Rutherford Clinical Category measured at Baseline, Day 30, Months 12 24 and 36.
- Functional outcome: comparison of the ankle brachial index (ABI) measurement at Baseline, within 30 days after index procedure, then at Months 12, 24 and 36.
- Incidence of reported stent fractures through 36 months.
- Operator assessment of device use

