### 5.3 Enrolment

All patients who provide written informed consent for the Study, meet all eligibility criteria and are treated with BioMimics 3D stent system will be considered enrolled in the Study. If the BioMimics 3D Stent System is inserted into the vasculature and treatment is attempted, but the procedure is aborted without delivery of a stent, only device failure and malfunction information and/or device related adverse events should be collected, if applicable.

Patients who are consented but the BioMimics 3D Stent System is not inserted into the vasculature will be considered screen failures. No data will be collected on screen failures.

Patients who are enrolled and treated, but who are later discovered to not meet all of the eligibility criteria will remain in the Study for follow-up and a Protocol Deviation form will be completed.

Patients who are enrolled and undergo staged treatment using BioMimics 3D Stent System in both limbs will be considered a single enrolment. Procedural information for both limbs will be collected.

For the purpose of this study, the point of enrolment is time of index procedure.

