### Table 1: Data Collection Schedule

Assessment	Baseline	Day 0 Index Procedure (Enrolment / Treatment)	Follow-up Visits 30 days (± 7 days), 12 months (365 days ± 30 days), 24 months (730 days ± 60 days), 36-months (1095 days ± 60 days)
Informed Consent	Х	-	
Medical History	х		х
ABI/TBI	X		х
Rutherford Clinical Category (RCC)	Х		х
Procedural data & technical success		X**	
Index procedure angiographic assessments		х	
Follow-up standard of care imaging assessments, as applicable: • Angiography • Duplex ultrasound • X-ray			х
Concomitant antiplatelet and anticoagulant medications	х	х	Х
Adverse Event Assessment		х	х
Subsequent intervention (target limb)		×	х
Device use questionnaire (operator)		Х	
Walking Impairment Questionnaire (WIQ)*	0		0

\*WIQ is optional (O) and may be collected if standard of care at site.

\*\* Females of childbearing potential should have a negative pregnancy test before procedure (according to site standard of care)

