### 6.3 Index Procedure

All procedures should be conducted in accordance with site standard of care and patient needs, there are no prohibited concomitant treatments. BioMimics 3D stent deployment shall be conducted in accordance with the IFU.

Data will only be collected on patients who have provided their consent and are treated, or treatment is attempted with BioMimics 3D stent system. All other patients will be considered screen failures and no data will be collected.

The following data will be collected at index procedure through to discharge:

- Lesion pre-treatment, e.g., PTA, drug-eluting balloon therapy, atherectomy, laser
- Baseline angiographic assessment, i.e., lesion size, inflow and outflow disease
- Stent placement: location, size and lot number/expiry of stent(s)
- Post-stenting treatment
- Assessment of final lumen patency via angiogram at the conclusion of the index procedure (percent angiographic stenosis)

- Procedure time
- Concomitant peripheral procedures
- Adverse events and device observations
- Device use questionnaire (completed by operator)
- Concomitant antiplatelet and anticoagulant medication

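### Acute technical and procedural success are planned only among patients who received a stent, and Section 5.3 restricts the data on aborted attempts in conflict with Section 6.3 and with the planned ITT outputs

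*Combined protocol and SAP*

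**What the plan says.** The objective in Section 3.1 reads: "The MIMICS-3D Study will evaluate safety, effectiveness and device performance within a real-world clinical population". Section 4.2 lists acute technical success and acute procedural success as secondary outcomes. The first is defined by a single measurement: "Acute technical success defined as the achievement of a final residual diameter stenosis", below a 30% threshold, when the procedure ends. The second adds freedom from a list of events within 72 hours. Neither definition names a denominator or mentions implantation.

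Section 9.4 assigns secondary endpoints to mITT and shows PP as a secondary analysis. Section 9.1 states for both sets: "Those subjects in whom the procedure is aborted without implantation of a stent will be excluded from this analysis set". ITT is used for the two primary endpoints as supportive information (9.1, 9.3) and for demographics and history (9.2). Section 9.1 also promises a description of everyone left out of mITT, with reasons for aborted procedures.

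On enrolment, Section 5.3 says that eligible, consenting patients who "are treated with BioMimics 3D stent system will be considered enrolled in the Study". Section 12 also counts patients in whom treatment was attempted, both as enrolled and in its ITT entry. Section 5.3 adds that a patient in whom the device "is not inserted into the vasculature will be considered screen failures".

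On data, Section 5.3 says that for a procedure aborted without a stent "only device failure and malfunction information and/or device related adverse events should be collected, if applicable". Section 6.3 covers consenting patients who "are treated, or treatment is attempted with BioMimics 3D stent system" and then lists the index-procedure data, including final percent stenosis on angiogram. Table 1 schedules "Procedural data & technical success" at Day 0. Neither states an exception for aborted cases.

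**The concern.** Acute success describes whether the procedure worked on the day. If attempts that ended without a stent are removed before the rate is calculated, the figure answers a narrower question: how often the result was good once a stent was in place. For a study with device performance among its objectives, the rate over all attempts is also needed, and the plan does not provide one.

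The second problem is data. The plan promises ITT tables and ITT analyses of the primary endpoints, while Section 5.3 bars collection of much of what they need for the patients who distinguish ITT from mITT. If 5.3 is followed, a 30-day MAE or a later CDTLR not judged device-related would go unrecorded in those patients, and Sections 9.3 and 9.7 rule out imputation. If 6.3 and 7.2.1 are followed, the data can exist and the restriction in 5.3 is wrong. The text does not say which applies.

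**Working it through.** **Step 1: which analyses include an aborted attempt?**

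| Output | Set (section) | Aborted attempts included? |
|---|---|---|
| Primary endpoints, main analysis | mITT (9.1, 9.3) | No |
| Primary endpoints, supportive | ITT and PP (9.1, 9.3) | ITT yes, PP no |
| Demographics and history | ITT, also mITT and PP (9.2) | In ITT |
| Acute technical and procedural success | mITT, PP (9.4) | No |
| Description of exclusions | Subjects outside mITT (9.1) | Yes, as a description and not as a rate |

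The separate DCB-cohort analysis (3.3, 9.1) names no analysis set, so it does not supply the missing denominator.

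**Step 2: are aborted attempts enrolled?** Section 12 says yes. Section 9.1 implies yes, because it forms mITT by removing them from enrolled subjects. Section 5.3 says only that treated patients are enrolled, and it reserves screen failure for patients without insertion. On its wording an aborted attempt is neither clearly enrolled nor a screen failure. Section 12 also requires all eligibility criteria to be met. Exclusion 1 concerns lesions that cannot be crossed and cannot be dilated enough for the delivery system to pass, so some failed attempts could fall outside even the Section 12 set.

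**Step 3: what is recorded for them?** Section 5.3 allows device failure or malfunction information and device-related adverse events only. Section 6.3 covers attempted patients and lists full procedural data. Section 7.2.1 requires all MAE, procedure-related events and target-limb vascular events through 36 months. Section 9.2 tabulates demographics and history for ITT. The clash with 6.3 is direct. Those with 7.2.1 and 9.2 follow if these patients are enrolled.

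**Step 4: possible size.** The plan gives no figure to reproduce and neither an abort rate nor a success rate. Assumptions: N = 500 attempts (the planned minimum enrolment), k aborted, x successes among the N − k implanted, and p = x/(N − k) of about 98%. Let a be the number of aborted lesions that nevertheless meet the stenosis criterion, from 0 to k.

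- mITT rate = x/(N − k)
- All-attempts rate = (x + a)/N
- With a = 0, or with aborts counted as failures by rule, the difference is p × k/N.
- With a = k, the difference is −(1 − p) × k/N, which is close to zero.

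Intervals are 95% Agresti-Coull, the method named in Section 9.3.

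| Aborted | mITT | All attempts, aborts as failures | All attempts, every aborted lesion meets criterion |
|---|---|---|---|
| 1% (5) | 485/495 = 97.98% (96.27 to 98.95) | 485/500 = 97.00% (95.07 to 98.21) | 490/500 = 98.00% (96.31 to 98.96) |
| 2% (10) | 480/490 = 97.96% (96.23 to 98.94) | 480/500 = 96.00% (93.87 to 97.43) | 490/500 = 98.00% (96.31 to 98.96) |

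The mITT figure is therefore higher by 97.98 − 97.00 = 0.98 or 97.96 − 96.00 = 1.96 points at one end, and lower by 0.02 or 0.04 points at the other. For p from 95% to 99%, the upper end is 0.95 to 0.99 points at 1% aborted and 1.90 to 1.98 points at 2%. At an assumed 5% (25 aborted) it is 466/475 = 98.1% against 466/500 = 93.2%, or 4.9 points. At 1% or 2% the shift is smaller than the mITT interval width of about 2.7 points.

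**The case against.** The written definition rests on residual stenosis and does not require a stent. Counting every abort as a failure therefore changes the endpoint, and a reader who infers that the mITT rate must overstate success by the abort share goes further than the documents allow. This stands: the effect is a range that starts at about zero.

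Device failures in aborted cases are not lost. Section 7.2.3 requires all malfunctions and performance issues to be reported, 5.3 keeps that information, and 9.1 describes the excluded subjects. This also stands. What is missing is a rate with a stated denominator and counting rule. In a descriptive study the reported proportion is the result, so this is more than a reporting preference.

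The enrolment conflict is one of wording. Section 5.3 does not say that aborted patients are not enrolled, and inferring that it does would be too strong.

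It can also be argued that 5.3 is the specific rule and overrides the general ones, and that 6.3 only limits who may contribute data. This does not rescue the plan. If 5.3 governs, Sections 9.1 to 9.3 promise ITT outputs for which the data may not be collected. Whether sites would in practice record different data cannot be judged, because the case report forms are not in the documents.

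**Conclusion.** The point holds. As planned, both acute-success rates are conditional on implantation and no all-attempts rate is reported. The data rule in 5.3 conflicts with 6.3. If aborted patients are enrolled, it also conflicts with 7.2.1 and 9.2 and leaves the supportive ITT analysis without MAE and CDTLR status, other than device-related events, for the patients that ITT adds.

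The size depends on an abort rate that the documents do not give and on a counting rule that the plan does not state for all attempts: 0 to about 1 point at an assumed 1%, 0 to about 2 points at an assumed 2%. A reader might infer that the 30-day MAE result is biased in a known direction. Nothing in the documents establishes a direction, and the choice of mITT as the primary set is not in dispute. The matter should be fixed because the correction is cheap and removes an ambiguity from a reported result.

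**What to change.** - **5.3:** Align the enrolment wording with Section 12 and 9.1. State that every patient in whom the device was inserted and treatment attempted stays in the all-attempts denominator, including any later found to meet exclusion 1.
- **5.3 with 6.3, 7.2.1 and 9.2:** Reconcile the data rules so that aborted attempts have already available baseline data, index-procedure data including final residual stenosis, and MAE status as available through 30 days. Otherwise state the exception in each place and report the number with unknown status in the ITT analyses.
- **9.4:** Report acute technical and procedural success over all attempts beside mITT, once by the written residual-stenosis definition and once with aborts counted as not successful.
- **9.1:** Keep mITT as the primary set.

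The cost is a few lines of text and data entry for a few patients (5 to 10 under the 1% and 2% assumptions). Consent already precedes the procedure, and Table 1 places the baseline assessments before it, although they are recorded only where standard of care provides them. The 30-day status may need an extra contact at some sites if it is not already available. The acute-success figure may be slightly less favourable.

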### 9.3 Primary Endpoint Analysis

Endpoints will be analysed using the modified intention-to-treat analysis set. An additional supportive analysis will be conducted in the ITT and PP analysis sets for the primary safety and effectiveness endpoints. All available data will be used for each endpoint and no imputations will be done.

The primary safety endpoint of MAE at 30 days will be presented as frequency and percentage and the 2-sided 95% confidence interval will be calculated via Agresti-Coull.

Similarly, the primary outcome measure for effectiveness, clinically-driven target lesion revascularisation (TLR) through 12 months, will be presented as frequency and percentage and the 2-sided 95% confidence interval will be calculated via Agresti-Coull.

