#### Dissection Classifications (National Heart, Lung and Blood Institute – NHLBI)

**Type A:** Small radiolucent area within the lumen of the vessel disappearing with the passage of the contrast material.

**Type B:** Appearance of contrast medium parallel to the lumen of the vessel disappearing within a few cardiac cycles.

**Type C:** Dissection protruding outside the lumen of the vessel persisting after passage of the contrast material.

**Type D:** Spiral shaped filling defect with our without delayed run-off of the contrast material in the antegrade flow.

**Type E:** Persistent luminal filling defect with delayed run-off of the contrast material in the distal lumen.

**Type F:** Filling defect accompanied by total coronary occlusion.

**Embolisation, Distal**: Any distal emboli confirmed by imaging.

**Embolisation, Symptomatic**: Clinical signs or symptoms of distal emboli detected in the treated limb distal to the treated lesion after the index procedure **or** noted angiographically and requiring mechanical or pharmacologic means to improve flow. This includes new abrupt occlusions or filling defects.

**Enrolment:** Subjects who are consented and meet all inclusion criteria and none of the exclusion criteria and are treated or treatment is attempted with the study device will be considered enrolled into the study.

**Haematoma**: Collection of blood (or its degradation products) which exceeds 5 cm in diameter, requires treatment, or prolongs hospitalisation.

Hypertension: Systolic BP >140 mmHg, or diastolic >90 mmHg requiring specific medical therapy.

**Hypotension:** Any prolonged systolic blood pressure <80 mmHg associated with symptoms and requiring intravenous vasopressor medications.

**Infection, access site:** Infection at the vascular access site, documented by lab culture or clinical evidence requiring medical treatment (irrigation, debridement, antibiotics, etc.) to resolve.

**Infection, systemic:** Systemic infection documented by positive lab culture or clinical evidence, requiring medical treatment to treat and resolve.

**Intention to Treat (ITT):** The principle of including outcomes of all subjects in the analysis who are enrolled and treated (attempted or completed) into the study, regardless of noncompliance, Protocol deviations, or withdrawal.

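### Section 5.3 restricts data on aborted attempts to device failures and device-related events, so 30-day MAEs judged procedure-related or unrelated can be missing from both the mITT and the ITT safety rate

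*Combined protocol and SAP*

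**What the plan says.** **Analysis sets.** Section 9.1 defines mITT as the set that "includes all enrolled subjects in whom the BioMimics 3D Stent System is implanted" and adds: "Those subjects in whom the procedure is aborted without implantation of a stent will be excluded from this analysis set". The per-protocol set carries the same exclusion. ITT is all enrolled subjects. The lead role goes to mITT ("While mITT is intended as the primary analysis set for all safety and effectiveness endpoints"), while "the primary safety and effectiveness endpoints will additionally be evaluated in the ITT and PP analysis sets as supportive information". Section 9.3 repeats this: "An additional supportive analysis will be conducted in the ITT and PP analysis sets for the primary safety and effectiveness endpoints". Sections 9.3 and 9.7 use available data and rule out imputation.

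**Data on aborted attempts.** Where the system enters the vasculature but no stent is delivered, Section 5.3 states that "only device failure and malfunction information and/or device related adverse events should be collected, if applicable". The same section counts as enrolled those who consent, are eligible and are treated. It does not name attempts.

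**Definitions elsewhere.** Section 12 counts attempted treatment as enrolment and describes ITT as "The principle of including outcomes of all subjects in the analysis who are enrolled and treated (attempted or completed) into the study". Sections 4.1.1 and 12 make MAE a composite of all-cause death, major amputation of the index limb and clinically-driven TLR. Under Section 7.1, the investigator judges whether an event is device-related or procedure-related.

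**The concern.** A safety rate restricted to implanted patients leaves out procedures that failed. That is acceptable if a second analysis shows what happened to those patients, and the plan assigns this job to ITT. The endpoint, though, does not depend on cause, while the 5.3 collection rule does. A death after a failed attempt that the investigator attributes to the procedure, or to something unrelated, is an MAE but is not on the 5.3 list. If it is not collected, ITT cannot show it and the Clinical Events Committee has nothing to adjudicate.

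The study is descriptive, so the estimated rate and its denominator are the result. A reader who sees similar mITT and ITT rates would take this as reassurance about failed attempts, when the similarity could simply reflect what was not collected.

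**Working it through.** **1. Which set can hold an aborted attempt?** Not mITT and not per-protocol, since both exclude it. ITT can, under the Section 12 definition of enrolment. Under the 5.3 wording (treated only), an aborted attempt might not be enrolled at all, and ITT would shrink to mITT.

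**2. What is collected on it under 5.3?**

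| 30-day event after an aborted attempt | MAE? | Collected under 5.3? |
|---|---|---|
| Death, major amputation or CDTLR judged device-related | Yes | Yes |
| The same, judged procedure-related | Yes | Not provided for |
| The same, judged unrelated | Yes | Not provided for |

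Section 9.7 accepts status learned later, but 5.3 provides no contact at which it would be learned.

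**3. Which sections disagree with 5.3?** Section 6.3 provides for data on patients in whom treatment is attempted. Sections 7.0 and 7.2.1 require every MAE to be recorded, with no exception for aborted attempts. Section 9.1 promises the reasons for aborted procedures. Section 9.2 promises demographics and history for all ITT subjects. Section 12 includes attempts in both enrolment and ITT.

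**4. The plan's own precision figures.** Section 9.6 gives 95% CI widths of 5.5% to 2% for an MAE rate of 90% to 99%. This appears to mean freedom from MAE, and the width is the same either way. At n = 500 the exact interval gives 5.46% and 1.99%; the planned Agresti-Coull interval gives 5.31% and 2.03%. The figures reproduce. They describe sampling error only and do not bear on the data gap.

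**5. Illustrative size.** The documents give neither an abort rate nor an event rate after an aborted attempt. Assumptions: N = 500 attempts; k = 10 or 25 aborted (2% or 5%); MAE risk m = 1-2% in implanted patients and a = 10-30% in aborted ones.

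All-attempts rate = [(500 − k)·m + k·a] / 500. The mITT rate is m.

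- Lowest: k = 10, m = 1%, a = 10%: (4.9 + 1.0)/500 = 1.18%, against 1.0%.
- Middle: k = 25, m = 2%, a = 20%: (9.5 + 5.0)/500 = 2.9%, against 2.0%.
- Highest: k = 25, m = 2%, a = 30%: (9.5 + 7.5)/500 = 3.4%, against 2.0%.

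The gap is (k/500)·(a − m). It runs from 0.02 × (10% − 2%) = 0.16 points to 0.05 × (30% − 1%) = 1.45 points.

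With rarer aborts (2 of 500, 10% risk) and 5 events in implanted patients, the rates are (5 + 0.2)/500 = 1.04% and 5/498 = 1.00%, which is negligible.

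**6. How much of this would ITT miss?** Let d be the share of aborted-patient events judged device-related. Missed events are k·a·(1 − d). In the middle case that is 5 of 14.5 events if d = 0, and none if d = 1. If aborted patients of unknown status drop out, ITT reads:

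- d = 0: 9.5/475 = 2.0%, the same as mITT.
- d = 1: (9.5 + 5)/(475 + 5) = 14.5/480 = 3.02%, slightly above the full-follow-up 2.9%.

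So ITT could fall anywhere from 2.0% to 3.02% around a true 2.9%, depending on attribution.

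**The case against.** The strongest reply is that the plan does not leave ITT empty. Section 5.3 keeps device-related events, and Section 7.1 extends these to deployment, operation, malfunction and user error. Section 7.2.3 requires every malfunction or failure to be reported promptly, and the committee adjudicates all MAEs and all potentially device-related events. Harm from the delivery system is therefore the part most likely to be captured. Sections 7.0 and 7.2.1 can also be read as covering every MAE on attempted cases.

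Much of this stands, and it rules out stronger readings that a reader might infer:

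- *ITT has no data on failed attempts.* It has device-related events.
- *ITT will agree with mITT whatever happened.* Step 6 shows otherwise.
- *Uncollected patients will be scored event-free.* That would in effect be imputation, which Sections 9.3 and 9.7 exclude.
- *Every device complication in Section 8.1 falls outside mITT.* An item such as "Partial stent deployment leading to surgical repair", or stent embolisation, involves a stent that has at least partly left the delivery system. The documents do not say how such a case is classified.

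The assumed rates may also be generous. CDTLR requires recurrent symptoms and new ischaemic signs, so bail-out treatment in the same session would not obviously count, and 10-30% would have to be mostly death or major amputation. The first exclusion criterion should limit aborts.

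What the reply does not remove is the word *only* in the one rule written for aborted attempts. A site following it has no reason to establish 30-day status.

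**Conclusion.** The point holds in a limited form. If sites follow 5.3, deaths, major amputations or CDTLR judged procedure-related or unrelated after an aborted attempt can be missing from both the mITT and the ITT 30-day MAE rate. Other sections point towards collecting them, so this is a contradiction about primary-endpoint data. It does not establish that the data will be absent.

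The size cannot be determined from the documents. Under the stated assumptions the all-attempts rate is 1.2-3.4% against 1-2% in mITT. This is an upper bound on what ITT would miss, since it treats every event in an aborted patient as uncollected. A fixed direction of bias in ITT is not supported. The point deserves correction because 30-day status not collected at the time cannot be reliably recovered later.

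**What to change.** 1. Use the Section 12 enrolment definition (treated or attempted) throughout, including 5.3, so that ITT cannot shrink to mITT.
2. Replace the restrictive sentence in 5.3. For every attempt, record the reason for aborting and 30-day status for all-cause death, major index-limb amputation and CDTLR, by telephone if needed. Align 6.3, 7.2.1, 9.1 and 9.2 with it.
3. In 9.3, report the ITT 30-day MAE rate beside the mITT rate, with the number of aborted attempts and how many have known 30-day status.
4. Preferably make ITT the lead set for 30-day safety and keep mITT for 12-month effectiveness. This is a matter of judgement, and items 1 to 3 stand without it.

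The cost is wording changes and one 30-day contact for a small number of patients (10 to 25 under the assumptions above). They have already consented, and Sections 3.4 and 6.1 already schedule a 30-day follow-up and allow telephone contact. Because those sections tie follow-up to site standard of care, the new text should say how the contact fits that limit. The reported MAE rate may become slightly less favourable.
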